5.1.2 Concomitant medication date imputation

5.1.2.1 Concomitant medication end date

To impute concomitant end date:

1. If the concomitant end date year value is missing, the date uncertainty is too high to impute a rational date. Therefore, if the concomitant end year value is missing or ongoing, the imputed concomitant end date is set to NULL.
2. Else, if the concomitant end date month is missing, the imputed end date should be set to the earliest of the following: study treatment follow-up period date, 31DECYYYY, date of death.
3. If the concomitant end date day is missing, the imputed end date should be set to the earliest of the following: study treatment follow-up period date, last day of the month, date of death.

If the imputed concomitant end date is less than the existing concomitant start date, use the concomitant start date as the imputed concomitant end date.

5.1.2.2 Concomitant medication start date

Concomitant treatments with partial start dates will have the date or dates imputed. Partial concomitant treatment start dates are imputed with reference to the first administration of study treatment within this study in accordance with the rules outlined below.

	Day	Month	Year
Partial Concomitant medication (CMD) Start Date	Not used	MON	YYYY
Treatment Start Date	Not used	TRTM	TRTY

The following matrix explains the logic behind the imputation.

Comparison of month section	MON missing	MON<TRTM	MON=TRTM	MON>TRTM
YYYY missing	(C) Uncertain	(C) Uncertain	(C) Uncertain	(C) Uncertain
YYYY<TRTM	(D) = 01JULYYYY	(A) = 15MONYYYY	(A) = 15MONYYYY	(A) = 15MONYYYY
	Before Treatment Start	Before Treatment Start	Before Treatment Start	Before Treatment Start
YYYY=TRTY	(C) Uncertain	(A) = 15MONYYYY	(C) Uncertain	(B) = 01MONYYYY
		Before Treatment Start		After Treatment Start
YYYY>TRTY	(E) = 01JANYYYY	(B) = 01MONYYYY	(B) = 01MONYYYY	(B) = 01MONYYYY
	After Treatment Start	After Treatment Start	After Treatment Start	After Treatment Start

The following table is the legend to the logic matrix.

Relationship	
Before Treatment start	Partial date indicates CMD start date prior to Treatment Start Date in this study
After Treatment start	Partial date indicates CMD start date after Treatment Start Date in this study
Uncertain	Partial date insufficient to determine relationship of CMD start date to Treatment Start Date in this study
Imputation calculation	
NC/Blank Uncertain	No convention
(A) Before Treatment Start	15MONYYYY
(B) After Treatment Start	MAX(01MONYYYY, Treatment Start Date +1)
(C) Uncertain	IF CMDTYP IN (1, 3) THEN Treatment Start Date -1

Relationship	ELSE IF CMDTYP IN (. 2) THEN Treatment Start Date +1
(D) Before Treatment Start	01JULYYYY
(E) After Treatment Start	01JANYYYY

To compute concomitant start date:

1. If the concomitant start date year value is missing, the imputed concomitant start date is set to one day prior to study treatment start date.
2. If the concomitant start date year value is less than the study treatment start date year value, the concomitant medication started before study treatment. Therefore:
 - a. If the concomitant month is missing, the imputed concomitant start date is set to the mid-year point (01JULYYYY).
 - b. Else if the concomitant month is not missing, the imputed concomitant start date is set to the mid-month point (15MONYYYY).
3. If the concomitant start date year value is greater than the study treatment start date year value, the concomitant started after study treatment. Therefore:
 - a. If the concomitant month is missing, the imputed concomitant start date is set to the year start point (01JANYYYY).
 - b. Else if the concomitant month is not missing, the imputed concomitant start date is set to the month start point (01MONYYYY).
4. If the concomitant start date year value is equal to the study treatment start date year value:
 - a. And the concomitant month is missing or the concomitant month is equal to the investigational treatment start date month, then the imputed concomitant start date is set to one day prior to investigational treatment start date.
 - b. Else if the concomitant month is less than the investigational treatment start date month, the imputed concomitant start date is set to the mid-month point (15MONYYYY).
 - c. Else if the concomitant month is greater than the investigational treatment start date month, the imputed concomitant start date is set to the month start point (01MONYYYY).

If complete (imputed) concomitant end date is available and the imputed concomitant start date is greater than the (imputed) concomitant end date, then imputed concomitant start date should be set to the (imputed) concomitant end date.

5.1.3 Other imputations

Medical history date of diagnosis imputation

Completely missing dates and partially missing end dates will not be imputed. Partial dates of diagnosis will be compared to the treatment start date.

- If diagnosis year < study treatment start date year and diagnosis month is missing, the imputed diagnosis date is set to the mid-year point (01JULYYYY)

- Else if diagnosis month is not missing, the imputed diagnosis date is set to the mid-month point (15MONYYYY)
- If diagnosis year = study treatment start date year and (diagnosis month is missing OR diagnosis month is equal to study treatment start month), the imputed diagnosis date is set to one day before study treatment start date

5.2 Statistical models

5.2.1 Primary analysis

Logistic regression model

The proportions of patients who achieve a PASI 90 response at Week 28 for each treatment group will be compared using logistic regression analysis. The model will include treatment and center as fixed effect and with covariates PASI score at baseline (Visit 2).

The SAS procedure PROC GLIMMIX will be used with the following SAS code:

```
proc glimmix data=.... order=internal;  
class trtn1 cntr ;  
model response = trtn1 cntr basv2 / ddfm=kr error=binary  
link=logit;  
lsmeans trtn1 / cl diff oddsratio;  
run;
```

where

response = PASI 90 response (= 1 or 0)

trtn1 = treatment

cntr = center

basv2 = PASI score at baseline (Visit 2)

The estimated odds ratios will be displayed along with the associated 95% confidence intervals and p-values (two-sided).

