ability to lose weight under these medications (weight gain is a well-known side effect of insulin and sulfonylurea agents/analogues). Patients with type 2 diabetes receiving other medications, such as DPP4 inhibitors, are allowed to participate in the study, as lifestyle intervention is the guideline-recommended basic therapy for any patient with type 2 diabetes (NVL Therapie des Type-2-Diabetes), and offers benefit for them, which outweighs the potential small risk of hypoglycemia or ketoacidosis in the case of metformin. The treating family physicians of the patients participating in the lifestyle intervention will be notified about the participation in the lifestyle intervention, so they can adequately monitor them and adjust their antidiabetic or antihypertensive medication.

Based on the current knowledge no interactions with negative consequences between Secukinumab therapy and lifestyle intervention can be expected. On the contrary, it is the goal of this study to assess potential positive effects of the combined application. The risk will be further minimized by close clinical and laboratory monitoring of participating patients at all study visit.

The additional risks of participating in the biomarker sub-study are those of blood sampling. Blood sampling will occur at time points where standard blood sampling is scheduled as well, and will not require additional venipuncture. Participation in the sub-study does not negatively affect the overall risk-benefit ratio for participation in the study.

4 Population

The study is conducted in Germany and the study population consists of a representative group of male and female patients (≥ 18 years old) with moderate to severe plaque-type psoriasis and concomitant metabolic syndrome according to International Diabetes Federation (IDF), American Heart Association (AHA), and National Heart, Lung and Blood Institute (NHLBI) consensus definition from 2009 (Alberti et al., 2009). The goal is to randomize a total of approximately 760 patients in approximately 100 sites in Germany. Considering analyses of prior studies and the inclusion criterion metabolic syndrome, a screening failure of 30 % is expected, making screening of approximately 1100 patients necessary in order to provide the required number of patients.

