5.3 Treatment assignment and randomization

Patients will be randomized in a 1:1 ratio to one of the two treatment arms at randomization visit. Randomization will be performed by the use of sealed envelopes. The investigator or his/her delegate will open the sealed envelope after confirming that the patient fulfills all ex- and inclusion criteria. The envelope will assign a randomization number to the patient, which can be used to link the patient to a treatment arm.

The randomization numbers will be generated using the following procedure to ensure that treatment assignment is unbiased and concealed from patients and investigator staff. A patient randomization list will be produced by the provider using a validated system that automates the random assignment of patient numbers to randomization numbers. These randomization numbers are linked to the different treatment arms.

The randomization scheme for patients will be reviewed and approved by a member of the Randomization Group.

At randomization visit an eligible patient will be given the lowest available randomization number. This number assigns the patient to one of the treatment arms. The investigator will enter the randomization number on the case report form (CRF).

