9.4.2 Statistical model, hypothesis, and method of analysis

The null hypothesis to be rejected is that the odds of response Week 28 are equal in both treatment groups. The corresponding alternative hypothesis is that the odds of response at Week 28 are higher under Secukinumab combined with lifestyle intervention compared to Secukinumab alone.

Let p_j denote the proportion of responders at Week 28 for treatment group j , $j=0, 1$, where

- 0 corresponds to Secukinumab combined with lifestyle intervention
- 1 corresponds to Secukinumab alone

The following hypotheses will be tested:

$H_0: (p_1 / (1 - p_1)) / (p_0 / (1 - p_0)) = 1$ versus $H_A: (p_1 / (1 - p_1)) / (p_0 / (1 - p_0)) \neq 1$

In other words:

H_A : The odds ratio of achieving a response at Week 28 for Secukinumab combined with lifestyle intervention vs Secukinumab alone is different from 1.

The primary analysis will be performed comparing treatments with respect to the primary efficacy variable in a logistic regression model with the factors treatment, center and covariate baseline PASI. The odds ratio and its 95% confidence interval (CI) and p-value will be given. The null hypothesis of equal odds will be rejected if the 2-sided p-value from the logistic regression model for the factor “treatment” is < 0.05 ; however, superiority of Secukinumab combined with lifestyle intervention will be claimed only if the direction is correct, i.e. if the odds of response are larger under Secukinumab combined with lifestyle intervention.

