Based on these considerations and the fact that we are looking at PASI90 response in the present study, we assume an absolute increase of 9% in PASI90 response in the Secukinumab combined with lifestyle intervention arm to 90% PASI90 responders compared to 81% PASI90 responders in the Secukinumab alone arm. An absolute increase of 9% in PASI90 responders would also be clinically meaningful.

Based on these assumptions 342 patients per arm would provide a power of 90 % at a two-sided alpha of 0.05 to demonstrate that the percentage of PASI90 responders at week 28 is higher in

the Secukinumab combined with lifestyle intervention arm compared to the Secukinumab alone arm. In case the true effect size would only be 7.5 %, this sample size would still provide a power of 75 %. To compensate for some expected drop out and/or premature discontinuations, 380 patients per arm are planned to be recruited for this trial.

10 Ethical considerations

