2.6 Analysis of secondary efficacy objective(s)

2.6.1 Analysis of secondary endpoints

PASI 75, 90 and 100 at weeks 1, 2, 3, 4, 8, 12, 16, 20, 24 and 28 will be analyzed analogous to the primary endpoint. Absolute PASI scores will be analyzed using a MMRM, with factors treatment, center, visit, visit*treatment interaction and covariate baseline PASI. The raw as well as the adjusted least squares means and their differences between treatment groups will be calculated for each visit together with their corresponding 95% confidence intervals and p-values.

The same MMRM model updated with relevant baseline covariate similar to primary endpoint will also be used for the analyses of the other continuous secondary endpoints hsCRP, HbA1c, fructosamine, fasting plasma glucose, LDL, HDL, total cholesterol, triglycerides, waist circumference, BMI, body weight, systolic and diastolic blood pressure, QoL-scores (Absolute DLQI total score, relative change from baseline of DLQI total score, absolute WHO-5 total score, relative change from baseline in WHO-5 total score, absolute self-assessed itch, pain, and scaling, relative change from baseline in self-assessed itch, pain, and scaling) and activity levels (steps per day).

All the patients reporting DLQI score = 0 or 1 will be considered as “Responders (0)”, whereas the patients reporting DLQI score ≥ 2 will be considered as “Non-responders (1)”.

Proportion of patients with DLQI score (0&1) i.e., DLQI responders will be evaluated in both the arms and will be compared using a logistic regression model with the factors treatment, center, visit, visit*treatment interaction and covariate baseline DLQI. The odds ratio and its 95% confidence interval (CI) and p-value will be reported. See [Appendix 5.3](#) for more details on PROs.

Note: For the subjects with fasting & non-fasting status, separate analyses will be performed for fasting plasma glucose, fructosamine, and HbA1c levels.

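### The primary logistic model fits about 100 fixed centre effects with about 7.6 patients per centre, so the nominal 5% test runs at about 6–7% and a real odds ratio is overstated.

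*SAP*

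**What the plan says.** Protocol 9.4.2 specifies a "logistic regression model with the factors treatment, center and covariate baseline PASI". SAP 2.5.2 repeats this for the FAS, and SAP 5.2.1 makes the role of centre explicit: "The model will include treatment and center as fixed effect and with covariates PASI score at baseline (Visit 2"). The GLIMMIX code there lists cntr in the CLASS and MODEL statements and has no RANDOM or STRATA statement. The null hypothesis is rejected if the two-sided p-value for treatment from this model is below 0.05, and superiority is claimed only if the direction favours the combination.

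On scale, Protocol Section 4 (Population) aims to "randomize a total of approximately 760 patients in approximately 100 sites in Germany". Protocol 5.3 says "Patients will be randomized in a 1:1 ratio to one of the two treatment arms at randomization visit" and describes no stratification by centre. The visible text has no rule for pooling small centres.

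The only sensitivity analysis for the primary endpoint is a CMH test stratified by centre (Protocol 9.4.4, SAP 2.5.4). SAP 2.6.1 says that PASI 75, 90 and 100 at ten visits "will be analyzed analogous to the primary endpoint". SAP 2.8 fits the same logistic model within each of three weight-loss subgroups.

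**The concern.** Unconditional maximum likelihood spends one nuisance parameter on each centre. When centres are small and their number grows with the sample, those parameters are never well estimated. The error carries over to the treatment effect: the log odds ratio is pushed away from zero when it is not zero, and the model-based standard error understates the true variability.

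What is at stake is the single confirmatory decision. The claim rests on this model's p-value, and this model supplies the headline odds ratio and confidence interval. Both errors favour finding and reporting an effect.

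**Working it through.** **Inputs from the documents.** 760 patients, about 100 sites, 1:1 allocation; PASI 90 response "to 90% PASI90 responders compared to 81% PASI90 responders in the Secukinumab alone arm" (Protocol 9.8); two-sided alpha 0.05, 90% power, 342 per arm, 380 recruited; missing week-28 PASI counted as non-response (SAP 2.5.3).

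**The plan's own sample size.** With p̄ = 0.855, the two-proportion formula gives n = [1.96·√(2·0.855·0.145) + 1.2816·√(0.81·0.19 + 0.90·0.10)]² / 0.09² = 320 per arm. The continuity correction, (n/4)·[1 + √(1 + 4/(n·0.09))]², raises this to 342, as stated. 342/0.90 = 380. The calculation is correct and takes no account of centre.

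**Sparsity.**
- Patients per centre: 760/100 = 7.6.
- Expected non-responders: 380 × 0.19 + 380 × 0.10 = 110, about 1.1 per centre.
- Planned odds ratio: (0.90/0.10)/(0.81/0.19) = 2.11.

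**Simulation of the planned model.** 760 patients and 100 centres; logistic maximum likelihood with fixed centre intercepts and a baseline covariate. Assumptions not in the documents: centre sizes equal or variable (gamma, shape 1.5), between-centre SD of 0, 0.5 or 1 on the logit scale, a baseline PASI effect of 0.2 per SD, and simple or block-of-4 allocation.

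Null, 81% in both arms, 8,000 replicates (Monte Carlo SE about 0.27 points):

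| Centres | Planned model | CMH | Mean model SE | Empirical SD |
|---|---|---|---|---|
| Equal, SD 0.5 | 6.55% | 4.93% | 0.220 | 0.239 |
| Variable, SD 0.5 | 6.51% | 5.25% | 0.215 | 0.230 |
| Variable, SD 0 | 6.24% | 5.10% | 0.211 | 0.224 |

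The SE shortfall accounts for the excess. In the second row 0.215/0.230 = 0.935, and 1.96 × 0.935 = 1.83 has a two-sided tail of 6.7%. Over all null scenarios run with 2,000 replicates the range was 5.5–7.25%. A separate run of 3,000 trials per scenario gave 6.1–7.1%, against 4.7–5.5% for CMH. Half of 6–7% is 3–3.5% in the favourable direction, against 2.5%; a direct count in another run gave 2.8–3.3%. The median odds ratio under the null was 1.00.

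Alternative, 81% against 90%, 4,000 replicates:

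| Centres | True conditional OR | Planned model, median | Mantel-Haenszel, median |
|---|---|---|---|
| Equal, SD 0 | 2.12 | 2.40 (+13%) | 2.13 |
| Variable, SD 0.5 | 2.17 | 2.39 (+10%) | 2.16 |

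The 3,000-trial run gave medians of 2.33–2.37 for a true 2.11.

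**With imputation.** The step from 342 to 380 implies about 10% loss. If that 10% is counted as non-response, the rates become 0.9 × 0.81 = 72.9% and 0.9 × 0.90 = 81.0%. Simulated type I error was then 6.0–6.5%, and the median odds ratio was 1.70 against 1.59–1.61, about 6% too high.

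**The replacement model.** Conditional logistic regression with treatment and baseline PASI, on simulated trials of the same size (4,000 null and 2,000 alternative trials per scenario, three scenarios), had type I error of 5.1%, 5.4% and 4.8% (Monte Carlo SE 0.35 points) and a median odds ratio of 2.12 for a true 2.11.

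**The case against.** The strongest reply is that the effect is modest and partly covered. Superiority can be claimed in one direction only, so the excess of false claims is about 0.5 to 1 percentage point. The centre-stratified CMH test is already pre-specified on the same endpoint and population and holds its level, so a discrepancy would be visible. The site count is only approximate: with 60 centres of skewed size, type I error was 5.8% and the median odds ratio 2.25 against 2.13. All of this stands and limits the size of the point. It does not remove it, because the decision is tied to the logistic p-value and the plan has no rule that adapts to the centres actually recruited.

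A reader might infer three stronger things.

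- **The model will fail to converge and force an unplanned choice.** This is not shown. A centre where everyone responds sends its own intercept to infinity, but the treatment estimate stays finite; no failure of that estimate occurred in the 3,000-trial run.
- **Many centres are wasted by this model.** About 0.855^7.6 = 30% of centres of average size would have no non-responder (0.77^7.6 = 14% with 10% imputed). Those centres carry no information on treatment under conditional logistic regression or CMH either, so the loss is no argument against the planned model.
- **The odds ratio is inflated whatever the truth.** It is not: at an odds ratio of 1 there is no bias, and the harm there is confined to the rejection rate.

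**Conclusion.** The point holds. With about 100 centres of about 7.6 patients, the confirmatory test runs at about 6–7% two-sided rather than the stated 5%. A true effect near the planned one is reported as a median odds ratio of about 2.3–2.4 instead of 2.11 with complete data, or about 6% too high with roughly 10% imputed as non-responders.

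This rests on the planned number of sites and on the assumed centre-size distribution, between-centre SD and allocation scheme. Inflation appeared throughout the ranges tried but shrinks with fewer, larger centres. The sample size calculation is not in question. The other responder endpoints and the weight-loss subgroups inherit the same model; the subgroup fits must be sparser still, but they are not confirmatory and the distortion there was not quantified.

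**What to change.** Replace the model in SAP 2.5.2 and 5.2.1 (and Protocol 9.4.2) with conditional logistic regression stratified by centre, and take the odds ratio, confidence interval and decision p-value from it:

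`proc logistic; class trtn1 / param=ref; strata cntr; model response(event='1') = trtn1 basv2; run;`

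Apply the same model to the other PASI responder endpoints in SAP 2.6.1. Keep the centre-stratified CMH test as the sensitivity analysis. Making CMH with the Mantel-Haenszel odds ratio primary is an acceptable alternative.

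The cost is a change of wording, one code block and some nominal power. With complete data, power fell from 94.7%, 96.2% and 94.1% to 92.7%, 94.6% and 92.6%, a loss of 1.5–2 points. With 10% imputed as non-responders it fell from 78.8% to 74.7% and from 80.1% to 77.3%, a loss of about 3–4 points. Part of each loss is the type I error returning to 5%. The lower level in the second case comes mainly from the imputation, which shrinks the difference to 81.0 − 72.9 = 8.1 points, and not from the change of model. The change should be fixed before the core analysis is run; afterwards it can only be reported beside the planned result.

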5.3 Patient reported outcomes (PRO)

PROs will be assessed by the following validated instruments.

- Dermatology Life Quality Index (DLQI®)
- Self-assessed pain, itching, scaling
- WHO-5

Dermatology Life Quality Index (DLQI®)

The DLQI® is a 10-item general dermatology disability index designed to assess Health-related quality of life (HRQoL) in adult subjects with skin diseases such as eczema, psoriasis, acne, and viral warts (Finlay and Khan, 1994; Basra et al., 2008).

The measure is self-administered and includes domains of daily activities, leisure, personal relationships, symptoms and feelings, treatment, and work/school. The measure is widely used: it has been tested across 33 different skin conditions and is available in 85 languages. The DLQI is the most frequently used instrument in studies of randomized controlled trials in dermatology. The recall period is the previous week, and the instrument takes 1 to 2 minutes to complete.

Each item has four response categories including 0 (not at all), 1 (a little), 2 (a lot), and 3 (very much). "Not relevant" is also a valid response and is scored as 0.

The DLQI[®] total score is the sum of the 10 questions. Scores range from 0 to 30, with higher scores indicating greater HRQoL impairment. Each subscale of the DLQI[®] may also be analyzed separately.

Meaning of DLQI Scores

- 0-1= no effect at all on subject's life
- 2-5= small effect on subject's life
- 6-10= moderate effect on subject's life
- 11-20= very large effect on subject's life
- 21-30= extremely large effect on subject's life

DLQI response 0/1 variable will be calculated based on the DLQI total score as follows:

- 0 – If DLQI total score is either 0 or 1
- 1 – If DLQI total score is > 1

DLQI percentage change from baseline will be calculated using DLQI total scores as follows:

$$((\text{post-baseline total DLQI} - \text{baseline total DLQI}) / (\text{baseline total DLQI})) * 100$$

Subject's self-assessed pain, itching and scaling

A self-administered, 11-point numeric rating scale (NRS, 0-10) will be used to evaluate the subject's assessment of their current pain, itching and scaling. Respondents will answer the following questions for the assessment of

- **Pain:** Overall, how severe was your psoriasis-related pain over the past 24 hours
- **Itching:** Overall, how severe was your psoriasis-related itch over the past 24 hours
- **Scaling:** Overall, how severe was your psoriasis-related scaling over the past 24 hours

Subjects have to rate their pain, itching, and scaling from 0 to 10 (11-point scale), with the understanding that the 0 represents the absence or null end of the pain, itching, or scale intensity (i.e., no pain, itching or scaling) and the 10 represents the other extreme of pain, itching, or scaling intensity (i.e., pain, itching or scaling as bad as it could be). The number that the patient selects represents his or her intensity score.

WHO-5

The 5-item World Health Organization Well-Being Index (WHO-5) is a validated, short questionnaire consisting of 5 simple questions, assessing subjective psychological well-being of the respondents. It is among the most widely used questionnaires for the assessment of psychological well-being and has been successfully applied across a wide range of study fields.

The measure is self-administered and takes approximately one minute to complete. The recall period is the previous two weeks. Each item has 6 response categories, ranging from 5 (“the whole time”) to 0 (“at no time point”). The WHO-5 total score is the sum of the 5 questions. Each subscale of the WHO-5 may also be analyzed separately.

